LVSD	Left Ventricular Systolic Dysfunction	
MHRA	Medicines and Healthcare Products Regulatory	
	Agency	
NHS	National Health Service	
NRES		
NYHA	New York Heart Association	
PI	Principal Investigator	
PSF	Pharmacy Site File	
QC	Quality Control	
R&D	Research & Development	
REC	Research & Development Research Ethics Committee	
RPT	Research Ethics Committee Renal Physiological Test	
SAE	Serious Adverse Event	
SAR	Serious Adverse Event Serious Adverse Reaction	
SD	Standard Deviation	
SDRN	Scottish Diabetes Research Network	
SGLT2		
SmPC	Summary of Product Characteristics	
SOP	Standard Operating Procedure	

SU	Sulphonylureas
SUSAR	Suspected Unexpected Serious Adverse Reaction
T2D	Type 2 Diabetes
TASC	Tayside Medical Sciences Centre
TCTU	Tayside Clinical Trials Unit
TG	Tubulo-glomerular
TMF	Trial Master File
U&Es	Urea & Electrolytes
UAR	Unexpected Adverse Reaction
UoD	University of Dundee

SUMMARY

Lay Summary

People with diabetes are at increased risk of developing Heart Failure (HF). Symptoms of HF include increased shortness of breath, reduced ability to exercise and in some cases premature death as the heart becomes less efficient at pumping blood around the body. Many of these symptoms are caused by fluid retention.

Drug options to treat HF in diabetes are currently limited as many of the drugs used are not suitable in diabetic participants as they cause unpleasant or harmful side effects. Many participants are given water tablets to help reduce or prevent fluid retention.

A new class of anti-diabetic drugs may have some benefit in HF with diabetes as they may reduce workload on the heart. It has been shown that they may also promote weight loss and increase exercise capacity in previous studies.

This trial will test if there is any benefit from using a drug called empagliflozin, (an SGLT2 inhibitor), to boost the effects of water tablets in diabetic participants with heart failure, by increasing sodium and urine output.

The findings of this trial may help to find out if this class of drugs, SGLT2 inhibitors, are useful in diabetic participants with HF.

In this trial, the aim is to recruit participants who have diabetes and heart failure. Participants will undergo investigations of kidney function, renal physiological tests, by measuring urine and sodium excretion.

As this is a two-way cross over clinical trial, participants will be randomly allocated to either empagliflozin 25mg (6 weeks) or a dummy medication (placebo) (6 weeks), with a two week wash-out period between each arm. This will allow the researchers to compare if there is a difference between normal treatment and the addition of empagliflozin. Participants will undergo renal physiological testing at the end of week 1 and week 6 during each arm. Participants will continue as normal with currently prescribed medication for their diabetes and heart failure.

Professional Summary

Men and women with diabetes have a 2-5 fold increased risk of heart failure (HF). The prevalence and incidence of HF is increasing in diabetes and mortality rates remain alarmingly high. This highlights the need for novel therapies in diabetes that will reduce HF risk and/or delay disease progression.

Type 2 Diabetes Mellitus (T2DM) and Chronic Heart Failure (CHF) is a common but lethal combination where therapeutic options are limited.

In CHF loop diuretics are a mainstay of therapy and are required to treat fluid retention. However, following their chronic use many people develop diuretic resistance leading to a worsening of CHF. Combining thiazide-like diuretics with loop diuretics is a commonly used but ineffective strategy to overcome diuretic resistance. Thus, new treatment strategies are urgently needed.

SLGT2 inhibitors, the newest class of anti-diabetic drugs, may have additional beneficial cardio-renal effects in participants with concomitant DM and CHF. SGLT2 inhibitors have an osmotic diuretic effect by reducing sodium and glucose absorption in the proximal tubules of the nephrons. We hypothesize that these effects could potentially be beneficial in treatment of participants with HF who are prone to sodium and fluid retention.

The aim of this trial is to assess the safety and efficacy of empagliflozin, an SGLT2 inhibitor, when prescribed in participants with DM and CHF who are on loop diuretics. We will conduct a double-blind, randomised controlled crossover trial of 34 participants with DM and stable CHF who are on furosemide. Participants will be randomised to either empagliflozin 25mg once daily or placebo for six weeks before crossing over to receive either placebo or empagliflozin for a further six weeks (after a 2 week washout period).

Participants will undergo detailed renal physiological assessment after 1 week of treatment and end of each treatment period to assess renal physiological parameters to ascertain whether the addition of empagliflozin in conjunction with an intravenous bolus of furosemide improves urine output without any significant adverse consequences. The primary endpoint of the trial is a change in urinary volume in response to furosemide with empagliflozin when compared to placebo.

If our hypothesis is confirmed, it may position SGLT2 inhibitors such as empagliflozin as a mainstay of treatment in participants with DM and CHF. Additionally, it may help to provide an understanding of some of the mechanisms that may provide an improvement in cardiovascular outcome with SGLT2 inhibitors shown in the recently published EMPA-REG¹⁵ trial.

1 INTRODUCTION

1.1 BACKGROUND

Chronic heart failure (CHF) and type 2 diabetes (T2D) frequently coexist. In population based studies and in CHF trials, the prevalence of T2D among participants with symptomatic heart failure (HF) is estimated to be between 12% and 41%.1 Among all participants hospitalised for CHF, it has been reported that up to 40% have T2D.^{2, 3} This association can be lethal since T2D has consistently been shown to be an independent predictor of increased morbidity and mortality in participants with CHF.4 However, treating participants with concomitant HF and T2D can be challenging. In the treatment of T2D, European Association for the Study of Diabetes/American Diabetes Association guidelines recommend tailoring therapeutic approaches to individual needs and/or risks.⁵ For most participants, metformin is the first choice anti-diabetic drug in all T2D participants including those with coincidental HF.⁶ This is underpinned by observational population cohort studies including our own observation in the Scottish population 7, 8. However metformin alone is often not enough to keep glycaemia under control and there is a substantial need for a second line anti-diabetic drug in HF participants. Unfortunately, the choices are very limited for the participants in this group. Sulphonylureas (SU) are commonly prescribed in T2D however they are associated with weight gain and hypoglycaemia, while there remain concerns that SUs may increase all-cause and cardiovascular-mortality,9 although this link is not fully established. Glitazones are contra-indicated in New York Heart Association III or IV HF, while their role in milder degrees of HF remains to a certain extent controversial with some observational studies indicating increased hospitalisation or readmission due to HF.¹⁰ Insulin use has also been associated with increased mortality in participants with CHF.¹¹ More recent agents such as the DPPIV inhibitors have also, disappointingly, failed to show cardiovascular benefit with some concerns raised following the publication of SAVOR-TIMI-53, that they increased HF hospitalisations, although these trials have only been of short duration¹² and may not apply to all DPPIV inhibitors (http://www.medscape.com/viewarticle/843830). Therefore, it can be concluded that therapeutic options in T2D and HF are very limited and there is a critical need for agents that will both improve overall glycaemic control and HF outcomes.

1.2 RATIONALE FOR TRIAL

In this trial it is proposed that there may be unique features of the SGLT2 inhibitors that exhibit renoprotective effects alongside cardioprotective effects in participants with mild-CHF with left ventricular systolic dysfunction and diabetes.

SGLT2 inhibitors have recently been licensed for use in participants with T2D. This oral anti-diabetic agent achieves its effect by blocking the low affinity, high capacity Type 2 Sodium-Glucose Linked co-Transporter, predominantly found in the proximal convoluted tubules of the kidneys, thus causing glycosuria, resulting in lowered blood glucose levels. SGLT2 inhibitors cause weight reduction following the caloric loss from glycosuria. They have also been shown to improve insulin resistance in ZDF rats¹³ and in a small clinical trial among T2D participants. 14 Exercise intolerance is a cardinal symptom of participants with HF and improving insulin sensitivity has been shown to improve exercise capacity. Thus, SGLT2 inhibition has the potential to improve exercise capacity in SGLT2 inhibition and to have beneficial effects on adverse left ventricular (LV) remodelling that occurs in participants with DM and HF by reducing the load on the heart through its diuretic and blood pressure lowering actions. The recent landmark EMPA-REG outcome trial that reported a striking 35% relative risk reduction in HF hospitalisations with empagliflozin may provide supportive evidence for beneficial effects of SGLT2 inhibition in the setting of CHF. 15, 16 However, it should be noted that in the EMPA-REG trial, only 10% of trial participants had HF. The currently recruiting, European Foundation for the Study of Diabetes funded REFORM Trial is examining the potential LV remodelling benefits of SGLT2 inhibitors in participants with T2D and HF (clinical trials.gov identifier NCT02397421).

A significant problem among participants with T2D and concomitant HF is diuretic resistance.¹⁷ It occurs frequently and can increase the length of stay in hospital and is associated with increased morbidity and mortality.¹⁸ The pathophysiology of diuretic resistance is varied and remains the subject of much debate.¹⁹ As a result, it is unclear how to treat diuretic resistance. At this time, sequential nephron blockade with thiazide-like diuretics used in combination with loop diuretics is often used to overcome diuretic resistance in acute decompensated CHF.²⁰ However this strategy does not always work and is associated with the hazards of hypokalaemia, hyponatraemia, hypotension and renal failure. A new strategy is needed. It is believed that SGLT2 inhibitors may be able to address this issue by its novel mechanism of action in the proximal part of

the renal tubules. It is hypothesized that its osmotic diuretic effects may augment the diuretic effects of furosemide in participants with T2DM and CHF.

There is data to support the potential for direct renoprotective actions arising from SGLT2 inhibition including actions to attenuate type 1 diabetes associated hyper filtration through an effect on tubulo-glomerular (TG) feedback which may have renal-protective effects by decreasing glomerular hydrostatic pressure.^{23, 24} SGLT2 inhibition has also been shown to attenuate tubular hypertrophy and reduce the tubular toxicity of glucose.²² They may also have indirect renoprotective effects through its blood pressure lowering effects and glycaemia lowering effects which could decrease the renal inflammatory and fibrotic response by blocking glucose entry into the cell.²² Consequently, there are now several on-going SGLT2 inhibitor renal outcome trials in T2D, including the CANVAS-R trial (clinicaltrials.gov identifier NCT01989754) and the CREDENCE trial (clinical trials.gov identifier NCT02065791). However, neither trial specifically looks at T2DM participants with CHF.

We contend that these effects, albeit modest, of SGLT2 inhibitors may potentially augment the diuretic effect of loop diuretics. It is noteworthy that osmotic diuretics such as mannitol have been used alone or in combination with loop diuretics such as furosemide to promote diuresis in participants undergoing intra-cranial surgery²⁸ and in the postoperative period to prevent acute kidney injury.²⁹ In CHF, mannitol was reported to promote effective diuresis in a single centre trial in the US.³⁰ Importantly, in all these settings, mannitol, which is a potent osmotic diuretic when used in combination with furosemide, was shown to be safe and did not result in renal failure or electrolyte disturbances.

It is known that increased sodium delivery to the macula densa following SGLT2 inhibition may intensify TG feedback and lead to a decline in glomerular filtration rate at least in T2D individuals.^{25, 26} A meta-analysis on the effect of dapagliflozin on renal function that included 12 placebo controlled randomized studies and involved more than 4000 participants with preserved renal function showed that dapagliflozin caused a fall in estimated glomerular filtration rate (eGFR) at week 1 that slowly returned to baseline.³¹ This pattern of acute eGFR decline followed by stabilization suggests that the acute eGFR decline reflects a (reversible) haemodynamic change rather than worsening of structural renal function.

The renal effects of SGLT2 inhibitors in combination with furosemide in T2D with CHF are not known. The recent EMPA-REG trial demonstrated a beneficial effect of the SGLT2 inhibitor empagliflozin on cardiovascular outcomes, particularly heart failure hospitalisation in T2D.¹⁵ It is thought that the most likely explanation for this positive result is the improvement in loading conditions caused by the osmotic diuresis.³³ Therefore, there is an urgent need for a trial to provide detailed acute and long-term information regarding the renal effects of the SGLT2 inhibition in combination with furosemide, in T2D participants with stable CHF.

The intent of this proposed trial is to obtain data that might be relevant to the design of future studies in which SGLT2 inhibitors may be considered as an adjunctive agent to loop diuretics in this vulnerable participant group. There is currently no data on combining SGLT2 inhibitors and diuretics, which is why this combination is not recommended at this point in time. However, it should be noted that in EMPA-REG 43% of participants were on loop diuretics. Since HF and T2D are frequent comorbidities, it is possible that physicians may find participants requiring both SGLT2 inhibitor therapy and furosemide concurrently. Only by trialling this, can these fundamental issues be addressed and, perhaps, inspire a change in practise.

We will recruit diabetic HF participants taking stable doses of furosemide, or, alternative loop diuretics, with eGFR greater than 45ml/min. Whilst SmPC states that empagliflozin should not be administered with an eGFR < 60 ml/min, EMPA-REG recruited participants with an inclusion criteria of eGFR ≥ 30 ml/min. 15 Within the total number of participants, n = 1819 (25%), with an EGFR < 60 mls/min, 1,212 were randomised to empagliflozin¹⁵. There was no reported increase in renal adverse events (acute kidney injury or hyperkalaemia) in those with eGFR < 60 mls/min regardless of whether the patients had impaired kidney function at baseline. Further analysis in the EMPA-REG renal outcome, demonstrated that in patients with T2D at high risk for cardiovascular events, those who received empagliflozin in addition to standard care had a significantly lower risk of microvascular outcome events than did those receiving placebo, a difference that was driven by a lower risk of progression of kidney disease (as defined by incident or worsening nephropathy).32 Furthermore the Dapa-HF trial (clinical trials.gov identifier NCT03036124) will set an inclusion of eGFR > 30mls/min to further evaluate the effect of dapagliflozin on the incidence of worsening HF or cardiovascular death in patients with CHF.

As there will be administration of intravenous furosemide of half the participant's usual daily dose with the RECEDE-CHF protocol, an eGFR ≥ 45 ml/min will be taken as a cut off for inclusion.

This trial will, with careful monitoring, begin the process of uncovering the unrealised potential of this new class of drug, and for the reasons given above, it is poised to become the 2nd line anti-diabetic agent of choice in HF participants.

2 TRIAL OBJECTIVES

2.1 OBJECTIVES

2.1.1 Primary Objective

The primary aim/objective will be to assess whether empagliflozin (SGLT2 Inhibitor) can augment the diuretic effect of loop diuretics in diabetic participants with mild CHF with left ventricular systolic dysfunction (LVSD), as measured by urinary volume, when compared to placebo.

2.1.2 Secondary Objectives

The secondary aims/objectives are to assess the effect of empagliflozin (SGLT2 inhibitor) on natriuresis when used with loop diuretics in diabetic patients with mild CHF with LVSD as measured by urinary sodium excretion, to measure the safety of add-on SGLT2 inhibitor therapy versus placebo on top of loop diuretics as measured by serum creatinine and eGFR, to assess effects of empagliflozin on protein/creatinine ratio, albumin/creatinine ratio and on the renal biomarker, cystatin C.

2.2 OUTCOMES

2.2.1 Primary Outcome

The primary outcome for this trial is:

To assess the effect of empagliflozin versus placebo on urine output

2.2.2 Secondary Outcomes

The secondary outcomes for this trial are:

- To assess the effect of empagliflozin versus placebo on urinary sodium excretion
- To assess the change in glomerular filtration rate (safety endpoint)

- To assess the change in creatinine (safety endpoints)
- To assess the effect of empagliflozin on protein/creatinine ratio
- To assess the effect of empagliflozin on albumin/creatinine ratio
- To assess the effect of empagliflozin on the renal biomarker, cystatin C.

3 TRIAL DESIGN

3.1 TRIAL DESCRIPTION

The RECEDE-CHF Trial is a single centre randomised, double-blind, placebo-controlled, crossover, trial conducted in NHS Tayside to compare the SGLT2 inhibitor empagliflozin 25mg, to placebo. Participants will be enrolled in the trial for a period of between 14 to 16 weeks.

At the screening visit, following informed consent, an initial medical history and clinical examination will be performed and concomitant medication will be recorded. Participants will have bloods taken for safety analysis and vital signs will be checked to confirm eligibility prior to enrolment. An assessment of suitability of the trial for the potential participant will be undertaken by the principal investigator or medically qualified delegate.

Should the participant meet the inclusion criteria and have no exclusion criteria identified, they will return for the baseline/randomisation visit at the Clinical Research Centre (CRC), Ninewells Hospital, Dundee, within four weeks post screening visit. Where possible the screening visit and randomisation visits will be combined.

At the randomisation visit participants will undergo safety blood tests, vital signs and trial medication will be dispensed (either empagliflozin 25mg or placebo).

Participants will continue on trial medication, empagliflozin 25mg or placebo, once daily, for a period of 6 weeks. Participants will be educated on the symptoms of hypoglycaemia which includes a written action plan on how to manage it in the unlikely event that it occurs.

Participants will return to the CRC 3-days (±2 days) post-randomisation, for a trial day, lasting approximately 5 hours, where they will have safety and research bloods drawn, vital signs recorded and will undergo renal physiological tests (RPT). Participants will be required to provide several urine samples throughout the course of the visit.

Participants will then return again at week 6 for a trial day, lasting approximately 5 hours, where they will undergo RPT again, safety and research bloods will be drawn and vital signs recorded. Participants will be again required to provide several urine samples throughout the course of this visit. Participants will terminate trial drug, either empagliflozin 25mg or placebo, at this visit and will return to the CRC at the end of the two week wash out period (week 9)

At week 9, participants will have safety and research bloods drawn, vital signs recorded, new trial medication dispensed, educated on the symptoms of hypoglycaemia and given a written action plan on how to manage it in the unlikely event that it occurs.

Participants will subsequently return to the CRC after 3 days (±2 days), for a trial day, lasting approximately 5 hours, where they will have safety and research bloods drawn again, vital signs recorded and will undergo renal physiological tests (RPT). Participants will be required to provide several urine samples throughout the course of the visit.

Participants will then return again at week 14 for the final trial day, lasting approximately 5 hours, where they will undergo RPT again, safety and research bloods will be drawn and vital signs recorded. Participants will be required to provide several urine samples throughout the course of the visit. Participants will terminate trial drug, either empagliflozin 25mg or placebo.

Further details of trial visits are detailed in section 7.1.

Participants not on insulin will continue with all usual medications, these remain unchanged throughout unless clinically indicated. Participants who are already on insulin at time of recruitment will be advised of the likelihood of having to reduce their total daily dose of insulin by for example by a reduction of 10% on the day they are randomised with an increase in the frequency of their blood sugar monitoring. Further dose titration will be done by the trial team, Diabetic Consultant, or GP with or without instruction from either the trial team or Diabetic Consultant, based on the participant's symptoms, home and laboratory-based blood sugar levels. Down-titration of therapy will be done in a stepwise manner starting with insulin. Other anti-diabetic agents will only be down-titrated once insulin has been discontinued. Up-titration of the IMP.

Acute exacerbations of CHF are likely to occur in the course of this trial. These will be treated as per usual practice and the empagliflozin or placebo will not need to be stopped unless the participant or their clinician specifically requests stopping or there are sound clinical reasons to do so. Anti-hyperglycaemic medications may be adjusted by the participants GP, hospital care consultant or PI as necessary during the trial; changes will be recorded in the concomitant medications.

It is expected that the number of participants requiring therapy changes will be equal between the two groups. Participants experiencing two or more severe hypoglycaemic episodes, requiring medical assistance, despite down titration or discontinuation of other anti-hyperglycaemic medications will have trial medication discontinued.

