3.2.3 Renal Physiological Tests

Participants will attend the Clinical Research Centre (CRC) on 4 separate trial days (2 while in each arm of the trial). On each trial day, participants will present themselves to the CRC, following an overnight fast. Two days before presenting to the CRC, participants will be required to follow a 2gm sodium and 2L fluid/day controlled diet. A 24-hour urine collection will be made in the 24 hours prior to the day of the renal physiological test. Participants will be asked to take their morning usual medications except their IMP (empagliflozin or placebo) and furosemide (or equivalent loop diuretic).

[figure not shown]
An intravenous cannula will be placed in each arm for subsequent infusion and blood sampling. Bloods will be drawn for measurement of plasma NT-proBNP (a biomarker of wall stress and will be measured as a discovery variable in this proof of concept trial) using standard protocols. Firstly, a 15 ml/kg oral water load will be administered over approximately a 15-minute period. Thereafter, at approximately 30 minute intervals, participants will be requested to void urine until the end of the trial day. The volume of urine passed will be measured and an aliquot stored for later analysis. On each occasion, the volume of urine passed will be measured, and an equal volume of water given to drink. In this way, a steady state diuresis will be established over approximately 3 hours. The last urine collection during this stabilization period will be taken as baseline. Approximately 3 hours after initiation of the test, each participant will receive an oral tablet of either empagliflozin 25mg or placebo. After the seventh urine sample, participants will be given a bolus of IV furosemide at half their total daily dose. Heart rate will be displayed continuously on an ECG oscilloscope and the blood pressure measured approximately every 60 minutes. Venous blood will be obtained at the midpoint of each clearance period for measurement of serum sodium, osmolality and creatinine. At the end of the RPT, light refreshments in the form of tea, coffee or juice with biscuits will be provided. A lunch will then be provided at the CRC.

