5.5.2 Treatment Allocation

Participants will be given blinded medication. At the randomisation visit they will be dosed with either empagliflozin 25mg (6 weeks) or matched placebo (6 weeks) to continue once daily, with a 2-week washout period between each arm. Participants and their bloods (including U&Es and LFTs, FBC) will be monitored as per trial schedule and medication stopped if concerns arise. If trial drug needs to be stopped

due to intolerance or adverse events, they will remain in the trial in order to do an "intention to treat" analysis. They will be invited to attend all future trial visits.

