6.3 DOSING REGIME

Participants will be given blinded medication. At the randomisation visit, they will be dosed with either oral empagliflozin 25mg OD or matched placebo to continue for 6 weeks, if tolerated. This will be followed by a two-week washout period. The participant will then cross over to be given either placebo or empagliflozin 25mg OD for a further 6 weeks.

No additional lifestyle restrictions will be imposed on the participant and we will ask them to carry on as normal except in the 48 hours preceding the renal physiological tests where we would request a 2gm sodium and 2L fluid/day controlled diet**DOSE CHANGES**

No dose change is planned in this trial. If the participant is taken off the trial, their GP and/or consultant will be informed of the reason for that.

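### The day 3 ±2 window lets the early renal test fall on day 1, when its 24-hour urine very likely starts before the first dose and, with combined screening and randomisation, its diet starts before consent

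*Protocol*

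**What the plan says.** **Window.** Protocol section 3.1 sets the period 1 visit: "Participants will return to the CRC 3-days (±2 days) post-randomisation, for a trial day". For period 2, after the week 9 dispensing visit, it says: "Participants will subsequently return to the CRC after 3 days (±2 days), for a trial day". Appendix 1 and SAP Table 1 give the same windows, with randomisation as Day 0.

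**First dose.** Protocol section 5.5.2: "At the randomisation visit they will be dosed with either empagliflozin 25mg (6 weeks) or matched placebo (6 weeks". No clock time is given.

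**Preparation.** Protocol section 3.2.3: "Two days before presenting to the CRC, participants will be required to follow a 2gm sodium and 2L fluid/day controlled diet". Section 6.3 gives the length of this restriction: participants carry on as normal "except in the 48 hours preceding the renal physiological tests". On urine, section 3.2.3 adds: "A 24-hour urine collection will be made in the 24 hours prior to the day of the renal physiological test". Appendix 1 says that the collection is completed in the 24 hours before the visit and brought to it. The IMP is withheld that morning and given at +150 minutes (Appendix 2).

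**Consent.** Section 3.1 prefers to combine the screening and randomisation visits where possible. Section 13.3.1 requires consent before any protocol-specific procedure.

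**Other statements of timing.** The Lay Summary says: "Participants will undergo renal physiological testing at the end of week 1 and week 6 during each arm". The Professional Summary says: "Participants will undergo detailed renal physiological assessment after 1 week of treatment". Section 3.2.1 labels visit 3 as day 2 for safety bloods and day 3 for research bloods. SAP section 5.1 says only that the tests were in the first and last week of each arm.

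**The concern.** The early visit is the trial's only source of information on the acute effect, and section 1.2 gives acute as well as longer-term renal information as a reason for the trial. If the early 24-hour collection includes hours before the first dose, its volume and sodium are not a clean on-treatment measurement. If the window permits a visit day on which the diet cannot be followed as written, sites must either break the preparation rule or begin a trial procedure before consent. No rule sets a minimum number of doses before the early test, and no analysis takes account of the actual test day. The summaries also describe a test at about day 7, which the window excludes, so a reader cannot tell which exposure the early result represents.

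**Working it through.** **Inputs.** The window is day 3 ±2, with Day 0 as the first dose (sections 3.1 and 5.5.2, Appendix 1). The test starts at 07:30 (section 9.1.1; SAP section 6 gives 08:30). Diet lasts 48 h and the collection 24 h (sections 3.2.3 and 6.3). *Assumed:* the Day 0 dose is taken at clock time t0 between 08:30 and 16:00. This is plausible because bloods, vital signs and dispensing all take place at that visit.

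**Window.** 3 − 2 = day 1 and 3 + 2 = day 5. Day 7 cannot be reached.

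**Formulas, for a test on day d at 07:30.**
- Diet start = test start − 48 h.
- Collection start = test start − 24 h.
- Prior doses = d, because that day's dose is held until +150 minutes.
- Share of the collection on treatment = (24d + 7.5 − t0) / 24, capped at 1.

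| Test day | Diet starts | Collection starts | Share on treatment | Prior doses |
|---|---|---|---|---|
| 1 | day −1, 07:30 | Day 0, 07:30 | 65% to 96% | 1 |
| 2 | Day 0, 07:30 | day 1, 07:30 | 100% | 2 |
| 3 | day 1, 07:30 | day 2, 07:30 | 100% | 3 |
| 4 | day 2, 07:30 | day 3, 07:30 | 100% | 4 |
| 5 | day 3, 07:30 | day 4, 07:30 | 100% | 5 |

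**Day-1 share.**
- t0 = 08:30: (31.5 − 8.5)/24 = 23/24 = 96%.
- t0 = 12:00: 19.5/24 = 81%.
- t0 = 16:00: 15.5/24 = 65%.
- With the SAP's 08:30 test start, each figure rises by 1/24, giving 69% to 100%.
- If section 3.2.3 means the previous calendar day, the collection runs from 00:00 to 24:00 on Day 0. The share is then (24 − t0)/24, that is 15.5/24 = 65% down to 8/24 = 33%.

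**Diet and consent.** With combined visits, consent is on Day 0. A day-1 test needs the diet from day −1, before consent. A day-2 test needs it from 07:30 on Day 0, also before consent if consent is taken later that morning. From day 3 there is no conflict. With separate screening, or at visit 7, the participant has already consented and can start the diet in time.

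**Exposure in the empagliflozin period.** Prior doses range from 1 to 5; counting the dose given during the test, 2 to 6, a ratio of 3. Drug level differs less. The documents give no half-life. Taking 8, 12 or 16 h as an assumption, the fraction of steady state after n daily doses is 1 − 2^(−24n/half-life). For n = 1 this gives 0.875, 0.75 and 0.646. For n = 5 it is at least 0.994. The ratio is therefore about 1.1, 1.3 and 1.5.

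**Analyses reached.** SAP section 5.4 takes the primary endpoint from the end-of-treatment 24-hour urine. Section 9 compares visits 5 and 9, and section 9.2 treats the secondary outcomes in the same manner. The early tests enter only through the repeated-measures ANOVA of the test days in section 9.2. No analysis of the early 24-hour collection is specified.

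**The case against.** The case on the other side is that day 1 is only the edge of a booking window, that the SAP's main analyses never use the early visit, and that each renal test has its own same-day, water-loaded baseline. A diet begun before the first dose is standardisation, not a fault. In the combined-visit case the 48-hour rule already rules out a compliant day-1 test. Most of this stands and limits the point to the early results. It does not remove the partly pre-dose collection on day 1, the clash between window and preparation rules, or the conflicting statements of timing.

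A reader might infer three stronger things that the documents do not support.

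- **Exposure differs five-fold between a participant's periods.** The 5 to 1 ratio counts capsules, and only one period contains drug. In the active period the drug-level ratio is about 1.1 to 1.5 on the assumed half-lives.
- **The treatment comparison is biased.** Sequence is randomised and blinded, and both periods have the same window. Nothing in the documents makes visit day differ systematically by treatment, so the supportable effect is added variability. A rule forcing visit 7 onto the same day as visit 3 is therefore not needed.
- **The primary result is affected.** The Professional Summary describes the primary endpoint as a furosemide response, which is measured only on test days. The SAP, however, fixes the primary endpoint as the 24-hour volume at the end of treatment.

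**Conclusion.** The point holds as a modest, cheaply corrected flaw in the scheduling of the early test. The pre-dose share of a day-1 collection, about 4% to 35%, rests on a 07:30 test start and an assumed Day 0 dose between 08:30 and 16:00. With the SAP's 08:30 start and an 08:30 dose it would vanish, so a pre-dose start is very likely but not certain. If the first dose were instead taken at home on day 1, prior doses would be 0 to 4. The diet-before-consent conflict is confined to visit 3 with combined screening and randomisation, on day 1 or day 2. The effect of 1 to 5 prior doses on urine volume cannot be sized from the documents. The disagreement between the window and the week-1 wording needs no assumption.

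**What to change.** - In Protocol section 3.1 and Appendix 1, and in SAP Table 1 to match, open the visit 3 and visit 7 window no earlier than day 2. For visit 3 with combined screening and randomisation, open it no earlier than day 3.
- Reconcile the Lay Summary, the Professional Summary and section 3.2.1 with that window.
- Record the actual test day, counted from the first dose in each period, and report its distribution by treatment.
- The SAP is written in the past tense, so visits may already have taken place. If any were on day 1, run a sensitivity analysis that excludes their 24-hour collections from any early-visit result.

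**Cost.** One booking day of five is lost per early visit, or two of five at visit 3 with combined visits. There are no extra visits, samples or participants, and dosing does not change.
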